UCG	Ultrasound Cardiogram

Trial title	An interventional, pilot study to evaluate the efficacy of oral nicorandil on improving microvascular function in female non-obstructive CAD patients (SPET study)
Trial number	EMR200505-506
Sponsor	Merck Serono Co., Ltd
Phase	IV
Trial center(s)/country(ies)	1(hospital)/1(country)
Planned trial period (first enrollment-last subject out)	Sep, 2016 - Oct, 2019
Trial objectives	
Primary objective:
 
To evaluate the improvement of microvascular function by positron emission tomography (PET) after twelve-week treatment of oral nicorandil in female no obstructive CAD patients;
 
Secondary objectives:
 
1) To evaluate the improve of myocardial blood flow (MBF) by rest and stress PET after twelve-week treatment of oral nicorandil
 
2)To evaluate the improve of heart function by echocardiography after twelve-week treatment of oral nicorandil
 
3) To evaluate the improve of angina attacks after twelve-week treatment of oral nicorandil

s	This is a single-center, interventional, pilot clinical trial. 11-20 patients will be enrolled in the treatment group who will take oral nicorandil 5mg, t.i.d for 12 weeks,. For all the patients, rest cardiac PET and stress cardiac PET will be tested at both screening period and end of study. Other laboratory parameters and clinical symptoms will be collected at baseline, 4 weeks, 8 weeks and 12 weeks of treatment. There will be 5 visits from the beginning to the end of the study

Planned number of subjects	11-20
Schedule of visits and assessments	
Screening visit: ECG, lab tests, MFR by rest and stress PET, UCG;
 
Visit 1(week 0): ECG, SAQ;
 
Visit 2 (week 4): ECG;
 
Visit 3 (week 8): ECG;
 
Visit 4 (week 12): ECG, lab tests, MFR by rest and stress PET, UCG


Diagnosis and main inclusion and exclusion criteria
	
Inclusion criteria:
 
 1. Female 2. Patients aged 18-70 years 3. Patients with typical stable angina but without coronary obstruction (defined as coronary occlusion<50%) by invasive coronary angiography or coronary computed tomography angiography (CTA) in recent three months⁵. All other long acting cardiovascular disease medicines, including but not limited to aspirin/clopidogrel, CCB, ACEI/ARB, β-blockers, statins, ivabradine, trimetazidine, et al, should be stable taken for at least two weeks before screening period 6. For patients who met these four criteria above, MFR will be tested by stress PET. Patients whose MFR <3.0 could be included in the study 
Exclusion criteria:
 
 1. Severe or uncontrolled hypertension (resting SBP \geq 160mmHg, or resting DBP\geq100mmHg at screening period) 2. Patients with shock (including cardiogenic shock), or hypovolemia 3. Severe hypotension (resting SBP<90mmHg , or resting DBP<60mmHg) 4. Significant valvular heart disease, congenital heart disease or cardiomyopathy 5. Congestive heart failure(NYHA III-IV), echocardiographic ejection fraction<45%
---	---

	
6. Acute pulmonary edema;
 
7. Hepatic or renal dysfunction, defined as:
 
 - Serum Alanine Aminotransferase (ALT) > triple of the normal value upper limit; - Serum Aspartate Aminotransferase (AST) > triple of the normal value upper limit - Serum creatinine > twice of the normal value upper limit 
8. Glaucoma
 
9. Active peptic ulcer or active skin ulcer
 
10. Taking glyburide, PDE-5 inhibitors, soluble guanylate cyclase stimulator(s)
 
11. Known to be hypersensitivity to nicorandil, nitrates, niacin, or any of the excipient
 
12. With contraindication to complete stress PET test
 
13. No legal ability and legal ability is limited
 
14. Patients unlikely to cooperate in the study or with inability or unwillingness to give informed consent
 
15. Child-bearing period women without effective contraceptive measures, pregnancy and lactation
 
16. Participation in another clinical trial within the past 30 days
 
17. Other significant disease that in the Investigator's opinion would exclude the subject from the trial

Investigational Medicinal Product (s): dose/mode of
	
Nicorandil (SIGMART® Tablets 5.0mg) / Oral / t.i.d, 12 weeks

administration/ dosing schedule	
Reference therapy(ies): dose/mode of administration/dosing schedule	
Patients have already received the current standard therapy strategy, if conditions permitted, aspirin/clopidogrel, ACEI/ARB, β-blockers, CCBs, and statins should be included;
 
All the medicines mentioned above and other anti-angina medicines(except nitroglycerine) need to be stabilized at least two weeks before screening period;
 
All subjects in treatment group will start taking nicorandil after enrollment. Subjects in standard treatment group will continue with all the medicines at the screening period. Nitroglycerine is allowed during the treatment period

Planned treatment duration per subject	12 weeks
Primary endpoint(s)	Comparison of myocardial blood flow reserve(MFR) between baseline and after twelve-week treatment
Secondary endpoint(s)	
Comparison of below items between baseline and after twelve-week treatment
 
1) MBF by rest and stress PET
 
2) Parameters of heart function by Echocardiography:
 
a) cardiac systolic function: Ejection Fraction (EF%), left ventricular end-systolic dimension (LVESD), left ventricular wall thickness
 
b) cardiac diastolic function: E/A ratio
 
3) Seattle Angina Questionnaire(SAQ) score

Statistical methods (includes sample size calculation)	For primary endpoint, when a sample size of 15, considering 30% drop out rate, will have 80% power to detect a difference in means of -0.55, assuming a standard deviation of differences of 0.56, using a paired t-test with a 0.05 two-sided significance level.

2 Sponsor, Investigators and Trial Administrative Structure

3.1 Background

3.1.1 Non-obstructive CAD

At least 20%-40% of patients presenting with angina have no significant CAD on invasive coronary angiography ^[1,2], when more women than men had no obstructive CAD (65% vs 32%)^[3]. Patients with stable angina and non-obstructive CAD have elevated risks of MACE and all-cause mortality ^[3]. Non-obstructive CAD comprised two groups: normal coronary arteries and those with <50% stenosis in any epicardial coronary artery. As many as about 65% of patients with chest pain without obstructive CAD are believed to have coronary microvascular dysfunction (CMD) ^[4].

3.1.2 Coronary microvascular dysfunction

3.1.2.1 Definition of coronary microvascular dysfunction

Coronary microvascular dysfunction defines as a primary dysfunction of the small coronary arteries <500µm in diameter which may cause microvascular angina or not ^[5]. It is attracting

more and more attentions now. In 2013 ESC guidelines on the management of stable coronary artery disease, it is listed as one of mechanisms of myocardial ischemia, together with fixed or dynamic stenosis of pericardial coronary arteries and focal or diffuse pericardial coronary spasm^[6]. The mechanism of CMD continues to be discussed. Functional abnormalities of the coronary microcirculation during stress, including abnormal dilator responses and a heightened response to vasoconstrictors, have been considered as potential mechanisms of chest pain and ischemic appearing ST-segment depression during exercise. Endothelial dysfunction is most probably only one of the components ^[5]

3.1.2.2 Patients with CMD have poor prognosis

Patients with CMD believed to have a poor prognosis, with higher rates of hospitalization and increase rates of adverse cardiovascular events, including sudden cardiac death, myocardial infarction, congestive heart failure, and coronary revascularization. The WISE study at 5.4-year follow-up demonstrated adverse events including cardiac death (53% being sudden cardiac death), stroke, and new onset heart failure rather than myocardial infarction, in particular in women with reduced Coronary flow reserve(CFR) assessed by adenosine^[7]. Murthy and his colleagues showed that a low myocardial flow reserve (MFR) (<1.5) was associated with a 5.6-fold increase in the risk of cardiac death in a population with 2783 patients ^[8].

3.1.2.3 CFR by PET is considered to be golden standard of non-invasive method for CMD assessment

Quantification of myocardial blood flow (MBF) and MFR has incremental values in the evaluation of the prognosis for patients with cardiovascular disease. There has been significant variation in the diagnostic criteria used to define CMD. The current gold standards for clinically assessing microvascular function have been CFR using invasive testing and positron emission tomography (PET) ^[9]. A CFR<2.0 strongly suggests coronary microvascular disease, and related to patients CV outcomes. However, CFR may be preserved in mild forms of coronary microvascular disease ^[5]. The current published data suggests that CFR are continuous variables, and thus, any cutoff used will have varying specificities and sensitivities. Several important prognostic studies have used thresholds of 1.5 to 2.3 to define cutoff values based on prognostic data ^[7,8]. However, many treatment studies have included subjects with CFR values >3 in their analysis. This study use a CFR<3.0 as a cutoff value for judging whether patient has coronary microvascular disease..

3.1.2.4 Limited treatment options for CMD

It is mentioned in the 2013 ESC guideline for the management of stable CAD that, symptomatic treatment is empirical. The results of available therapeutic trials cannot be accepted as conclusive because of variable patient selection, small sample size, inadequate design and lack of demonstration of clinical improvement of microvascular disease. All patients should receive secondary prevention medications including aspirin and statins. β -blockers are recommended as a first line treatment. Calcium antagonists are recommended if β -blockers do not achieve sufficient symptomatic benefit or are not tolerated. ACEI is recommended in patients with refractory symptoms ^[6]. Nicorandil is also recommended by

the guideline with the evidence that improvement of exercise capacity has been observed in a small trial with nicorandil which will be described in section 3.1.3.2.

3.1.3 Nicorandil has special effect on microvascular function

3.1.3.1 Mechanism of nicorandil's effect on microvascular function

Nicorandil is a unique dual pharmacological mechanism anti-anginal agent with adenosine triphosphate sensitive potassium (K_{ATP}) channel agonist and nitrate-like properties. It opens K_{ATP} channels in the vascular smooth muscle cell, leading to K^+ efflux and membrane hyperpolarization, which in turn reduces Ca^{2+} influx, including closing voltage-sensitive calcium channels (VOC). Its K_{ATP} channel opening effect also inhibits Ca^{2+} release from the sarcoplasmic membrane. The concentration of intracellular free Ca^{2+} then decreases. Arterial vasodilation is therefore predominant^[16]. K_{ATP} channel is one of the most critical target spots that regulates the tone of coronary arterioles (with diameter < 200 μ m)^[17].

3.1.3.2 Evidences of nicorandil's effect on microvascular function

A study result on dogs showed that the vessels < 100 μ m in diameter were more sensitive to nicorandil than vessels > 100 μ m. ATP-sensitive potassium channels are involved in the nicorandil-induced dilation of vessels smaller than 100 μ m^[18].

In a study to assess the role of nicorandil in vasodilation of human coronary resistance vessels in vitro. Coronary resistance vessels were resected from the right atrial appendage of 27 patients undergoing open heart surgery. Nicorandil induced a concentration-dependent vasodilation in these coronary resistance vessels^[19].

In a randomized, double-blind, placebo-controlled, crossover study, 13 patients with microvascular angina, (defined as had chronic stable angina, an ischemia-like ECG during exercise, normal angiography, no evidence of coronary spasm, and coronary flow reserve < 3.0 by invasive Doppler assessment), were studied to find out if their cardiac ischemia could be improved after 2 weeks of oral nicorandil (5mg, t.i.d). Treadmill exercise tests and 24-hour ambulatory electrocardiogram monitoring were performed. The results showed that both time to 1-mm ST depression and total exercise duration were significantly prolonged with nicorandil treatment compared with placebo, suggesting that nicorandil might have a direct vasodilatory effect on coronary microvasculatures in patients with microvascular angina^[20].

Till now, there were no clinical trials to investigate nicorandil's effect on microvascular function by intuitive, visible and quantitative imaging test.

This clinical trial will be conducted in compliance with the clinical trial protocol, Good Clinical Practice (ICH Topic E6, GCP) and the Japanese ministerial ordinance on GCP, and any other applicable regulations.

3.2 Risk-benefit assessment

- a. The pre-clinical, clinical-pharmacological and clinical results together form a rational basis for the planned clinical trial.
- b. The risk-benefit relationship has been carefully considered in the planning of the trial. Based on the pre-clinical and clinical data available to date, the conduct of the trial is considered justifiable using the dose(s) and dosage regimen(s) of the Investigational

Medicinal Product (IMP) as specified in this clinical trial protocol. The trial shall be discontinued in the event of any new findings that indicate a relevant deterioration of the risk-benefit relationship and would render continuation of the trial unjustifiable.

- c. Based on the pre-clinical and clinical data available to date, the conduct of the trial is regarded as justifiable at the planned dose ranges.
- d. Besides the study drug nicorandil, all patients need to undergo rest and stress PET test both at baseline and end of treatment. Cardiac PET is more and more widely used now for cardiac diagnosis, prognosis assessment and efficacy assessment of response to therapy^[21]. The patient radiation exposure is significantly less with most PET perfusion radiotracers than SPECT. In our study, the radiotracer will be N-13 ammonia (dose for baseline/EOT: 10-20mCi), when 10 mCi of N-13 ammonia exposes the patients to only 1.5 mSv^[21]. That is much less than the radiation dose of a CT coronary angiography exam (16 mSv is the average adult effective dose from a CT coronary angiography exam), or an interventional fluoroscopy (5-70 mSv)^[22]. For the stress PET, ATP will be used as hyperemic agent. ATP has been approved with good safety and tolerability in previous trials^[23,24]. For patients who suffer from angina with all current standard therapies but no obstructive coronary, the free test of microvascular function in this study may avoid them from further more coronary CTA or interventional coronary angiography;

4 Trial Objectives

Primary

To evaluate the improvement of microvascular function by positron emission tomography (PET) after twelve-week treatment of oral nicorandil in female non-obstructive CAD patients

Secondary

- 1) To evaluate the improvement of myocardial blood flow (MBF) by rest and stress PET after twelve-week treatment of oral nicorandil
- 2) To evaluate the improvement of heart function by echocardiography after twelve-week treatment of oral nicorandil
- 3) To evaluate the improvement of angina attacks after twelve-week treatment of oral nicorandil

5 Investigational Plan

5.1 Overall Trial Design and Plan

The study is a single-center, interventional, pilot study.

5.1.1 Major aspects of the trial

There will be a 2-week screening period, when baseline lab tests, ECG, UCG and PET will be conducted in this period. Patients who met the inclusion criteria but not the exclusion criteria will be enrolled. Totally 11-20 patients will be enrolled in the study. The study period after enrollment is 12 weeks. The anticipated recruitment period is 12 months. The anticipated period of the whole study will be 15 months. According to the recruitment

[figure not shown]
progress, if there have been 11 patients complete their following period, this study could be accomplished when meet the end of the anticipated period of the whole study.

Patients in the nicorandil group will start to take nicorandil 5mg, t.i.d from visit 1 for 12 weeks. All other cardiovascular medicines which need to be stabilized at least two weeks before screening period will be continued. Patients in standard treatment group will still take all the cardiovascular medicines stabilized at least two weeks before screening without any other newly added drugs. There will be a visit every four weeks. Symptoms and safety issues will be assessed at visit 2, visit 3. At visit 4 (week 12, end of treatment), lab tests, ECG, UCG, PET, symptoms and safety issues will all be re-assessed.

The primary endpoint is the MFR tested by PET at baseline and end of treatment; the secondary endpoints include the MBF by rest and stress PET at baseline and end of treatment, the heart function at baseline and end of treatment (based on UCG), symptom and quality of life at baseline and end of treatment (based on Seattle Angina Questionnaire).

In order to collect all the information in the inclusion and exclusion criteria for subjects' enrollment, medical history, physical examination, lab tests, ECG and UCG should be conducted in a 2-week screening period. As MFR by PET is also an inclusion criteria, rest and stress PET should also be conducted in subjects who have already met all other inclusion but not exclusion criteria in this 2-week screening period. If patients conducted lab tests, ECG or UCG in this period, but not especially for this trial, the result could also be used for the screening. 20 patients who meet the inclusion criteria but not the exclusion criteria will be enrolled in the study.

5.1.2 Schematic diagram of the study plan

5.2 Discussion of Trial Design

This is a single-arm, interventional, pilot study. PET is chosen for the assessment of primary endpoints. It is thought to be golden standard for the assessment of microvascular function due to its excellent image and able to quantification^[9]. Nicorandil is believed to improve microvascular function due to its unique effect on K_{ATP} channel of vascular smooth muscle as

detailed described in section 3.1.3.1. Many Cardiologist also found nicorandil's good efficacy on patients with suspected coronary microvascular dysfunction in their clinical practice. However, there are few clinical evidences to show nicorandil's effect on microvascular function, especially by intuitive, quantitative imaging test. Also, PET is only limitedly used in CAD patients in China. As there was no MFR data test by PET in coronary microvascular dysfunction patients in China before, no reliable data could be provided for a RCT study design. In order to investigate nicorandil's effect on microvascular by PET, and to collect more information and parameters for further studies, this interventional, pilot study is designed.

5.2.1 Inclusion of Special Populations

Only female patients are enrolled in this study, because women are more likely to suffer from non-obstructive coronary artery disease than men ^[3]. Some other studies focus on CMD, such as WISE study ^[7], also only enrolled women in the study.

5.3 Selection of Trial Population

5.3.1 Inclusion Criteria

For inclusion in the trial, all of the following inclusion criteria must be fulfilled:

1. Female
2. Patients aged 18-70 years
3. Patients with typical stable angina but without coronary obstruction (defined as coronary occlusion <50%) by invasive coronary angiography or coronary computed tomography angiography (CTA) in recent three months
5. All other long acting cardiovascular disease medicines, including but not limited to aspirin/clopidogrel, CCB, ACEI/ARB, β -blockers, statins, ivabradine, trimetazidine, et al, should be stable taken for at least two weeks before screening period
6. For patients who met these five criteria above, MFR will be tested by stress PET. Patients whose MFR <3.0 could be included in the study

5.3.2 Exclusion Criteria

Subjects are not eligible for this trial if they fulfill any of the following exclusion criteria:

1. Severe or uncontrolled hypertension (resting SBP \geq 160mmHg, or resting DBP \geq 100mmHg at screening period)
2. Patients with shock (including cardiogenic shock), or hypovolemia
3. Severe hypotension (resting SBP <90mmHg, or resting DBP <60mmHg)
4. Significant valvular heart disease, congenital heart disease or cardiomyopathy
5. Congestive heart failure (NYHA III-IV), echocardiographic ejection fraction <45%
6. Acute pulmonary edema;
7. Hepatic or renal dysfunction, defined as:
 - Serum Alanine Aminotransferase (ALT) > triple of the normal value upper limit;
 - Serum Aspartate Aminotransferase (AST) > triple of the normal value upper limit
 - Serum creatinine > twice of the normal value upper limit
8. Glaucoma
9. Active peptic ulcer or active skin ulcer

10. Taking glyburide, PDE-5 inhibitors, soluble guanylate cyclase stimulator(s)
11. Known to be hypersensitivity to nicorandil, nitrates, niacin, or any of the excipient
12. With contraindication to complete stress PET test
13. No legal ability and legal ability is limited
14. Patients unlikely to cooperate in the study or with inability or unwillingness to give informed consent
15. Child-bearing period women without effective contraceptive measures, pregnancy and lactation
16. Participation in another clinical trial within the past 30 days
17. Other significant disease that in the Investigator's opinion would exclude the subject from the trial

5.4 Criteria for Initiation of Treatment with the Investigational Medicinal Product

The inclusion and exclusion criteria examined at screening shouldn't be checked again before initiation of the treatment.

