6.3 Assignment to Treatment Groups

After completion of all the screening evaluations, 20 eligible subjects will be enroll to treatment group.

Subject numbers should be unique (i.e. reallocation of subject numbers is not permitted).

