7.1 Schedule of Assessments

Day 1 is defined as the first day of enrollment.

The trial procedures and assessment contents are as follow:

1. Screening Visit -Day -14 to 0: this visit entails the following:

Before any procedures that are related to the trial is undertaken, informed consent of the patient should be obtained. Thereafter, basic information of the patient will be obtained and patients are screened for eligibility based on the inclusion and exclusion criteria.

- a) Record birth date, gender, height, weight, waist circumference, current medical condition and past medical history, including concomitant therapies
- b) Perform physical examinations, including vital signs (blood pressure, heart rate)
- c) ECG: heart rate; sinus rhythm/arrhythmia, specify; cardiac hypertrophy(yes/no); abnormal ST-T change(yes/no),if yes, specify;
- d) Echocardiography
- e) Rest and stress PET
- f) Blood tests: full blood count (white blood cells, neutrophils, red blood cells, hemoglobin and platelets), myocardial enzymes(CKMB), liver function (ALT, AST), renal function (Bun, Cr), fasting blood glucose and blood lipids (TC, TG, LDL-C and HDL-C), electrolyte (K, Na) (data within -28 days of liver function, renal function, fasting blood glucose and blood lipids are accepted)
- g) Routine urine test (PH, Specific gravity, Protein, Glucose, Ketone, Nitrite, Leukocytes, Hemoglobin, Red blood cells, Bilirubin), urine pregnancy test
- h) Signing the informed consent form
- i) AE
- j) Concomitant medication

2. Visit 1- Day 1±3: this visit entails the following:

- a) Enrollment.
- b) Perform physical examinations, including vital signs (blood pressure, heart rate)
- c) ECG: heart rate; sinus rhythm/arrhythmia, specify; cardiac hypertrophy(yes/no); abnormal ST-T change(yes/no),if yes, specify;
- d) Seattle Angina Questionnaire score;

- e) Cardiovascular events: cardiac death, hospitalization caused by heart failure/ACS/revascularization, stroke, cerebral hemorrhage;
- f) AE;
- g) Concomitant medication

3. Visit 2- Day 28±3: This visit entails the following:

- a) Perform physical examinations, including vital signs (blood pressure, heart rate
- b) ECG: heart rate; sinus rhythm/arrhythmia, specify; cardiac hypertrophy(yes/no); abnormal ST-T change(yes/no),if yes, specify;
- c) Record adverse events, concomitant drugs and use of study drug;

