9.3 Subject Identification and Privacy

A unique subject number will be assigned to each subject at inclusion, immediately after informed consent has been obtained. This number will serve as the subject's identifier in the trial as well as in the clinical trial database.

The subject's data collected in the trial will be stored under this number. Only the Investigator will be able to link the subject's trial data to the subject via an identification list kept at the site. The subject's original medical data will be accessible for the purposes of source data verification by the Monitor, audits and regulatory inspections, but the subject's confidentiality will be strictly maintained.

Data protection and privacy regulations will be observed in capturing, forwarding, processing, and storing subject data. Subjects will be informed accordingly, and will be requested to give their consent on data handling procedures in accordance with national regulations. For subject registration, the investigator will fill out the subject registration form completely and send it to the subject registration center by fax.

When it is confirmed that the subject meets all inclusion criteria and does not meet any of the exclusion criteria, the subject registration center registers the subject and informs the Investigator and the Sponsor of the registration number by fax. If the subject is ineligible for the trial and is therefore not given a registration number, a subject number is allocated and documented.

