Appendix I Schedule of Assessments

	Screening visit (Day -14 to 0)	Visit 1 (Day 1±3)	Visit 2 (Day 28±3)	Visit 3 (Day 56±3)	Visit 4 (Day 84±3)
Signing the ICF	×				
Demographic data	×				
Inclusion and exclusion criteria	×				
Medical history	×				

Body weight and height	×				×
Waist circumference	×				×
Vital signs	×	×	×	×	×
Physical examination	×	×	×	×	×
ECG	×	×	×	×	×
Full blood count	×				×
Hepatic and renal functions	×				×
Blood glucose and lipids	×				×
Echocardiography	×				×
Rest and stress PET	×				×
SAQ		×			×
Cardiovascular events		×	×	×	×
Sigmat® therapy (For treatment group only)		×	×	×	×
Adverse event record	×	×	×	×	×
Medication possession ratio (MPR)	×				×
Concomitant medicine	×	×	×	×	×

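### Section 5.4 tells the site not to re-check eligibility before the first dose, so no rule stops nicorandil being started in a patient whose Visit 1 findings newly meet a safety exclusion such as severe hypotension

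*Protocol*

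**What the plan says.** Section 5.4 is headed as the criteria for initiating treatment, but it sets no criterion. Its single sentence is: "The inclusion and exclusion criteria examined at screening shouldn't be checked again before initiation of the treatment".

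The surrounding text fits that sentence:

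- Section 5.1.1 states "Patients who met the inclusion criteria but not the exclusion criteria will be enrolled" and places the tests that inform eligibility in the 2-week screening period.
- Section 6.3 states "After completion of all the screening evaluations, 20 eligible subjects will be enroll to treatment group".
- Section 7.1 screens for eligibility at the screening visit (Day -14 to 0) and lists enrollment as the first item of Visit 1 (Day 1±3).
- Appendix I has a row "Inclusion and exclusion criteria" that is marked at screening and nowhere else.

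Dosing begins at the next visit: "Patients in the nicorandil group will start to take nicorandil 5mg, t.i.d from visit 1 for 12 weeks". Section 7.1 has Visit 1 collect vital signs, physical examination, ECG, the angina questionnaire, cardiovascular events, adverse events and concomitant medication. It attaches no action to any of these results.

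**The concern.** Some exclusions in 5.3.2 describe states that can appear between screening and the first tablet. The clearest is exclusion 3, severe hypotension (resting SBP <90 or DBP <60 mmHg). Shock or hypovolemia (exclusion 2), NYHA class III-IV failure (part of exclusion 5) and acute pulmonary edema (exclusion 6) are of the same kind.

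The protocol itself shows why low blood pressure matters for this drug. Section 3.1.3.1 describes arterial dilation as the main vascular effect of nicorandil. Section 6.5.2 prohibits PDE-5 inhibitors and soluble guanylate cyclase stimulators because of added hypotension when they are given with it.

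The same reading therefore has different consequences on two occasions. At screening, a DBP below 60 mmHg makes the patient ineligible. At Visit 1, just before her first dose, the reading is taken and recorded, and 5.4 tells the site not to compare it with the criterion. What is at stake is subject safety at the first dose.

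**Working it through.** No sample-size or error-rate calculation bears on this. The check compares the texts and works out two intervals from the visit windows.

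**1. Does any rule bar the first dose at Visit 1 when an exclusion is newly met?**

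| Newly met condition | Governing text | Effect |
|---|---|---|
| Pregnancy | 5.5.2 | withdrawal required |
| Prohibited drug | 5.5.2, 6.5.2 | withdrawal |
| PCI or CABG | 6.5.3 | withdrawal |
| Severe hypotension, shock, hypovolemia, pulmonary edema, NYHA III-IV | 5.5.2, exclusion-criterion rule | withdrawal only if the investigator and/or sponsor judges it necessary |
| Any of these recorded as an adverse event | 5.5.2, adverse-event rule | withdrawal if the investigator and/or subject wants it or judges it necessary |

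The first three rows are covered. For the last two, the only provisions are discretionary, and they govern withdrawal from the drug. They are not conditions for starting it. Exclusion 17 gives the investigator general discretion, but it is itself an exclusion criterion, so 5.4 applies to it too.

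**2. How old can the screening check be at the first dose?**

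Inputs from 7.1: screening Day -14 to 0; Visit 1 Day 1±3, that is Day 1-3 = -2 to Day 1+3 = 4. From 5.1.1: dosing starts at Visit 1.

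- Longest gap = latest Visit 1 day minus earliest screening day = 4 - (-14) = **18 days**.
- If the first dose is fixed on Day 1, the range is 1 - 0 = 1 day to 1 - (-14) = 15 days. That reading is open because 7.1 says "Day 1 is defined as the first day of enrollment", but it ignores the printed ±3 window.
- The lower end of the Visit 1 window (Day -2) overlaps the screening window, so the shortest gap is not fixed by the windows.
- Liver, renal, glucose and lipid results are accepted from Day -28, so these can be 4 - (-28) = 32 days old.

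**3. How long until blood pressure is next scheduled?**

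Input from 7.1: Visit 2 at Day 28±3, that is Day 25 to 31.

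- First dose on Day 1: 28 - 1 = 27 days, range 25 - 1 = 24 to 31 - 1 = 30.
- With the Visit 1 window as well: 25 - 4 = 21 to 31 - (-2) = 33 days.

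On either reading, a patient who starts with low blood pressure has no scheduled re-measurement for at least three weeks.

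**The case against.** A reader might infer that 5.4 contradicts 5.1.1, 7.1 and 9.3, because enrollment takes place at Visit 1 and only eligible patients may be enrolled. The documents do not support that. Section 5.1.1 puts the eligibility assessments in the screening period, 7.1 lists enrollment at Visit 1 without an eligibility step, and 6.3 and Appendix I tie the criteria to screening. Section 9.3 registers a subject "When it is confirmed that the subject meets all inclusion criteria and does not meet any of the exclusion criteria", but does not say at which visit or on which data, so it cannot be set against 5.4. Nor can one imagine different sites following different sections, since the trial has one hospital.

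A second temptation is to argue that exclusion 3 must apply at Visit 1 because, unlike exclusion 1, it is not limited to the screening period. That qualifier is also absent from most other criteria, including the laboratory limits in exclusion 7, which before dosing are tested only at screening. Its absence proves little.

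The strongest remaining defense has three parts:

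- **Wording.** The word shouldn't may have been meant as need not, and the protocol's English makes this plausible. On that reading the review before dosing is optional, not discouraged. It is still not required, and a reader of the literal text cannot tell which was meant.
- **Clinical judgment.** Nothing in 5.4 compels dosing. A competent investigator would be expected to withhold a vasodilator from a patient in shock or pulmonary edema. This stands for the dramatic cases. It is weaker for a borderline reading, such as a DBP just under 60 mmHg in a patient who feels well, where an explicit rule is most useful.
- **Existing safeguards.** The Visit 1 data are collected, adverse events are recorded from consent onward, and 5.5.2 allows withdrawal. This stands too, and is why the point is small. These safeguards still leave the decision discretionary and frame it as withdrawal, where a condition for starting is needed.

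**Conclusion.** The point holds as a minor defect in a stated rule. Followed literally, 5.4 allows nicorandil to start at Visit 1 in a patient whose Visit 1 blood pressure already meets exclusion 3, with only discretionary withdrawal provisions to prevent it. The eligibility check may then be up to 18 days old, using the printed Visit 1 window, or up to 15 days if the first dose is fixed on Day 1. Blood pressure is next scheduled 21 to 33 days after the first dose if both visit windows are used, and 24 to 30 days after if the first dose is on Day 1.

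The conclusion assumes that the first dose is taken at Visit 1, as 5.1.1 says, and that shouldn't is read as written. It is limited to exclusions that can change and are not already handled by 5.5.2 (pregnancy), 6.5.2 (prohibited drugs) or 6.5.3 (PCI/CABG). The protocol gives no basis for estimating how many patients would be affected. The primary MFR estimate is not biased by this.

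**What to change.** Replace the sentence in 5.4 with wording such as:

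> Before the first dose, the investigator reviews the data collected at Visit 1 against the exclusion criteria that can change, notably severe hypotension and new acute conditions, and does not start nicorandil if one is met. Laboratory tests, echocardiography and PET need not be repeated.

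Add a mark at Visit 1 in the eligibility row of Appendix I, and a checkbox in the CRF to record that the review was done.

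The cost is a short amendment. No new test, threshold or visit is needed, because everything to be reviewed is already collected at Visit 1. The downside is that a few patients who have already had a PET scan may not start treatment. Under 8.4 a patient who never takes a dose is outside both the ITT and the safety population, so holding her back adds no missing outcome to the analysis; the loss is one recruit and one scan.
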